-At visits Entry, week 4 and week 10 study medication will be dispensed by the study staff. Subjects will be asked to return all study medication at each visit and the remaining medication will be counted by the study team and returned to the investigational pharmacy. The study team will assess adherence and record in source document. Adherence will be calculated based on the number of pills dispensed and returned. Study staff will also note in the source document if patients report missed doses. Once a patient arrives at their scheduled visit, the study team will fax a prescription to the Investigational pharmacy who will receive the elemental zinc medication in bulk and dispense per patient when they arrive at their scheduled visit.

- The zinc will be purchased from Lee Silsby Compounding Pharmacy. It will be delivered directly to our investigational pharmacy at University Hospitals. The pharmacy will store the zinc according to their regular procedures, and will dispense study drugs at the time of each study follow up visits, and the number of dispensed pills will be based on the randomization arm.

TOXICITY MANAGEMENT

Only toxicities related to study drugs (zinc) will be considered. Toxicities felt to be unrelated to study drugs will be left to the discretion of the primary care provider of the study participants. AACTG grading system will be used for evaluation for Grading Adult Adverse Experiences.

-Subjects who develop a new Grade 1 adverse event or toxicity may continue study drug without alteration of the dosage. Subjects experiencing Grade 1 adverse event who choose to withdraw from the study should be encouraged to complete the study evaluations as outlined in the Schedule of events.

- For all toxicities of Grade 2 thought to be related to the study drug, the study medication can be held at the discretion of the local investigator. If unable to resume it within 3 weeks, then the subject will be taken off study drugs but will continue to be followed and undergo the evaluations as per schedule of events.

- For all toxicities Grade 3 thought to be related to study drug, study medication will be held until the toxicity grade returns to \leq Grade 2 or to the entry value. If unable to resume study drugs for longer than 3 weeks, then the subject will be taken off study drugs but will continue to be followed and undergo the evaluations as per schedule of events.

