- For any Grade 4 toxicity (confirmed X 2 values for laboratory abnormalities) regardless of the cause, subjects will be taken off study drugs but will continue to be followed and undergo the evaluations as per schedule of events. Exceptions are asymptomatic elevation of indirect bilirubin in subjects receiving indinavir or atazanavir therapy, asymptomatic elevation of CPK, or elevations in lipid levels.

CRITERIA FOR PERMANENT STUDY DISCONTINUATION

-Request by the subject to withdraw

-At the discretion of the IRB

-Pregnancy or breast-feeding

[figure not shown]
-Request of the primary care physician if s/he thinks the study is no longer in the best interest of the subject.

STATISTICAL CONSIDERATIONS

The primary Aim of this pilot study is to demonstrate that oral dosing of zinc can impact a biological signature in patients with HIV. Biological signatures (hs-CRP, sCD14, sTNF-RI, LBP) will be assessed to determine if giving the natural product (zinc gluconate at 45 mg and 90 mg) to patients with HIV results in a meaningful change in the measure.

Inter-assay variability less than 15% are generally acceptable¹¹. To reduce this variability we will repeat each of these assays twice (run in duplicate) and compute average from the repeated assays performed in the same lab under same conditions conducted by the same technician. Given this set-up, the bioassays will efficiently quantify the biomarkers with less than 6% inter-assay variability which is substantially less than the general acceptable guidelines. Moreover, this inter-assay variability should be equivalent in both sets of measures obtained at baseline and after the Zinc supplementation.

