As the transmission of HIV and other blood-borne pathogens can occur through contact with contaminated needles, blood, and blood products, appropriate blood and secretion precautions will be employed by all personnel in the drawing of blood and shipping and handling of all specimens for this study, as currently recommended by the Centers for Disease Control and Prevention and the National Institutes of Health.

All infectious specimens will be packaged and sent in accordance with requirements mandated by the International Air Transport Association Dangerous Goods Regulations- Packing Instruction 602.

DATA SAFETY AND MONITORING PLAN

This is a pilot study that will serve to collect preliminary data on the anti-inflammatory effects of zinc in HIV. However, an independent data and safety monitoring board will be established to include an independent HIV expert, a statistician, and a community advocate. The DSMB will meet every 6 months (or earlier as needed) to review safety data and adverse events. The DSMB will function to: review and approve plans for data and safety monitoring for this trial; to review data on a timely basis and to ensure proper conduct and progress of study; to review credentials of investigator and project staff; to make recommendations to project investigator and staff regarding issues of concern; to address adverse events. The DSMB will meet twice a year in Cleveland, Ohio or by phone conferences to review study protocols progress, and safety data. Meetings will be held in an open format, except if privileged data are discussed. At the time of the continuing review, the DSMB report will be prepared by [name] and her staff and will include enrollment and dropout rates, protocol deviations, subjects symptoms, review of clinical and laboratory results.

The DSMB will review interim data to detect evidence of adverse events to determine if the trial should continue as originally designed, should be changed or even stopped based on the data. The DSMB will evaluate the progress of the trial, including periodic assessments of the recruitment goals, protocol adherence, accrual and retention of participants. The DSMB will protect confidentiality of the study subjects.

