The Principal Investigator will report all > Grade 2 adverse effects deemed to be possibly, probably or definitely related to study participation to the University Hospitals Cleveland Medical Center CWRU IRB within one week in writing. All >1 Grade 1 adverse effects deemed to be possibly, probably or definitely related to study participation will be collected. The Principal Investigator, investigators, and study nurse will prepare every year an update to renew the University Hospitals Cleveland Medical Center CWRU IRB approval of the clinical studies. In this renewal, investigators will inform the IRB about adverse effects Grade > 1 noted during the performance of the study. Accrual, retention, and data quality and timeliness will be monitored by the Principal Investigator.

Protocol Deviations: All deviations will be documented in the source document and the IRB will review all protocol deviations. Any deviation that may affect study conduct or safety will promptly be reported within 72 hours.

Quality Control Committee: Not applicable

Adverse Events

Definitions

The definitions of Adverse Events (AEs) and Serious Adverse Events (SAEs) are given below. It is of the utmost importance that all staff involved in the study be familiar with the content of this section. The principal investigator is responsible for ensuring this.

Adverse Event

An Adverse Event (AE) is the development of an undesirable medical condition or the deterioration of a pre-existing medical condition following or during exposure to a pharmaceutical product, whether or not considered causally related to the product. An undesirable medical condition can be symptoms (eg, nausea, chest pain), signs (eg, tachycardia, enlarged liver) or the abnormal results of an investigation (eg, laboratory findings, ECG). In clinical studies, an AE can include an undesirable medical condition occurring at any time, including run-in or washout periods, even if no study treatment has been administered.

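### Adverse-event collection and the one-week IRB report are limited to events judged related, and meeting the serious adverse event definition triggers no report to the IRB or DSMB

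*Combined protocol and SAP*

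**What the plan says.** All references are to the combined protocol and SAP.

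- **Collection** (Data Safety and Monitoring Plan): "All >1 Grade 1 adverse effects deemed to be possibly, probably or definitely related to study participation will be collected".
- **Expedited report** (same section): "The Principal Investigator will report all > Grade 2 adverse effects deemed to be possibly, probably or definitely related to study participation". This goes to the IRB in writing within one week.
- **Annual update** (same section): "In this renewal, investigators will inform the IRB about adverse effects Grade > 1 noted during the performance of the study". No relatedness condition is attached.
- **DSMB** (same section): "The DSMB will meet every 6 months (or earlier as needed) to review safety data and adverse events". The report prepared for the board lists symptoms and clinical and laboratory findings. It does not name SAEs.
- **Definition of an adverse event** (Adverse Events, Definitions): an undesirable condition counts "whether or not considered causally related to the product". The text adds that any worsening after a participant enters the study qualifies.
- **SAE definition**: the usual seriousness criteria, an exclusion for disease progression, and a statement that investigators will assess causality. The subsection headed Reporting of Adverse Events, which follows, deals only with recording diagnoses in preference to symptoms.
- **Safety endpoint** (Study Endpoints): the percentage of participants with events above Grade 2 that are possibly or probably related to study drug.
- **Toxicity Management**: "Only toxicities related to study drugs (zinc) will be considered"; later in the same section, "For any Grade 4 toxicity (confirmed X 2 values for laboratory abnormalities) regardless of the cause", participants come off study drug.

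**The concern.** The definitions and the operative rules do not match. Staff are told that an adverse event is an adverse event whatever its cause, and then that the events to be collected are those judged related. Someone following the collection sentence would build a safety dataset already filtered by a judgement. The SAE criteria are set out in full, but nothing follows from meeting them except a further judgement of cause.

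Safety and tolerability are a stated secondary objective. Both arms receive zinc, so no untreated group shows the background rate, and attribution is hard for any single event. Comparing all events between the 45 mg and 90 mg arms is the adverse event analysis that does not rely on attribution. It needs events to be recorded before anyone decides what caused them. For the individual participant, the issue is whether a serious event reaches the IRB and the DSMB in time for either to act.

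**Working it through.** The plan gives no figure on this point to reproduce. The check sets the rules side by side and follows different kinds of event through them.

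**Step 1. Collection against definition.** The collection sentence requires relatedness; the definition excludes relatedness as a condition. An event judged unrelated is an adverse event under the second and is not required to be collected under the first. The annual update adds a third scope: grade above 1, no relatedness filter. It asks for events that the collection sentence does not oblige anyone to gather. The threshold >1 Grade 1 could mean above Grade 1, Grade 1 and above, or more than one Grade 1 event.

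**Step 2. Routes for an event that meets the SAE definition.**

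| Serious event | Collection sentence | One-week IRB report | Annual IRB update | DSMB |
|---|---|---|---|---|
| Related, above Grade 2 | Covered | Yes | Yes | Next meeting |
| Related, Grade 2 | Covered, subject to the unclear threshold | No | Yes | Next meeting |
| Related, Grade 1 | Unclear | No | No | Next meeting, if collected |
| Unrelated, Grade 2 or above | Not covered | No | Yes, if noted | Next meeting, if collected |
| Unrelated, Grade 1 | Not covered | No | No | Next meeting, if collected |

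Only the first row has an expedited route, and it comes from grade and relatedness, not seriousness. No row has an individual notification to the DSMB between meetings. The board may meet early, but nothing in the text tells it that a serious event has occurred.

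**Step 3. Is there a route elsewhere?** The disease-progression exclusion says which events are not to be reported as SAEs. That presupposes a reporting route, but none is written. The deviation rule has a clock ("Any deviation that may affect study conduct or safety will promptly be reported within 72 hours"), but a serious event is not in itself a protocol deviation.

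**Step 4. Possible delay.** Inputs: DSMB every 6 months, IRB renewal every year, 16 weeks per participant.

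- DSMB, if no early meeting is called: 6 months = 52/2, about 26 weeks; 26 − 16 = 10 weeks longer than the whole treatment period.
- Annual IRB renewal: up to 52 weeks; 52/16 = 3.25 treatment periods.

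These are maximum waits under the written schedule, not expected ones.

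**Step 5. Toxicity Management.** One sentence limits consideration to zinc-related toxicity; another acts on Grade 4 toxicity from any cause. These conflict directly. Both concern management of toxicity and study drug, not collection. The link to the collection rule is by implication: an any-cause Grade 4 rule cannot be applied or audited unless Grade 4 events of any cause are captured.

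**The case against.** The other side has several sound points.

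- The collection sentence says that related effects will be gathered; it does not say that others are discarded. Visits at weeks 4, 10 and 16 ask about symptoms or changes in health, and haematology and chemistry are drawn at every visit in both arms. Much of the raw information would therefore exist. This stands, and it is why the loss is a risk and not a certainty. But it is the only sentence that says which events are collected, and a symptom answer or a laboratory value is not an event recorded with grade, seriousness and causality.
- A reader might infer that events are reported only if judged related. The documents do not support that: the annual IRB update and the DSMB review carry no relatedness filter.
- A reader might infer that serious events are left out of safety review. That also goes too far. The board reviews safety data and adverse events and may meet early. Serious events are not excluded; their inclusion is not guaranteed and their timing is not set.
- A reader might infer that the collection rule contradicts the Grade 4 rule. The Grade 4 sentence governs stopping study drug, so its direct conflict is with the other toxicity sentence.
- A reader might wish to calculate how high a true event rate could lie behind zero related events. That needs an assumed share of drug-caused events correctly attributed, and the documents give no basis for one.

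All-cause events by dose are also not the only attribution-free safety evidence, since the laboratory results are another. With two active arms of 25, they show only effects that differ between doses.

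**Conclusion.** The concern holds in this form. Collection wording and the expedited IRB report are restricted to events judged related, which conflicts with the protocol's causality-free definition and with its own annual update. No recipient or deadline is given for an SAE anywhere. Of the five kinds of serious event traced above, four have no expedited route to the IRB, and none has one to the DSMB. The wait could reach about 26 weeks for the board and 52 weeks for the IRB, against 16 weeks on study.

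This is more than missing detail, because following the written rule would give an attribution-filtered safety dataset in a trial without placebo. The conclusion assumes that staff apply the collection sentence as written and that no unscheduled board meeting is called. It does not depend on any assumed rate of misattribution, and how many events would be lost cannot be estimated from the documents.

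**What to change.** 1. In the Data Safety and Monitoring Plan, replace the collection sentence: all adverse events as the protocol defines them, from study entry, are recorded with grade, seriousness and causality, whatever the attribution. Remove the unreadable threshold. Starting at study entry matters because the definition covers events before any dose, and participants may start zinc up to two days after randomisation.
2. Make the SAE definition operative: every SAE, whatever its grade or attribution, is reported to the IRB and to the DSMB within a time limit that the sponsor states, and such a report can prompt an early DSMB review.
3. Tabulate all-cause adverse events and SAEs by randomised arm alongside the existing related-event endpoint. The A-versus-B labels already planned for the statistician preserve blinding.
4. Separately, the sponsor should reconcile the two Toxicity Management sentences on related-only and any-cause toxicity. Which rule should apply is a clinical decision and is not proposed here.

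The cost is protocol wording and modest extra adverse event recording in 50 participants over 16 weeks. Symptoms and laboratory results are already gathered at the visits, so no new procedure is needed.

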HOMA-IR ($r=0.58$; $p<0.0001$), sCD14 ($r=0.19$; $p=0.018$), sCD163 ($r=0.23$; $p=0.005$), hs-CRP ($r=0.30$; $p<0.0001$); IL-6 ($r=0.20$; $p=0.017$), and sTNF-RI (0.26; 0.0015). The study did not measure visceral abdominal fat or whole body measurements, but nonetheless support the hypothesis that central fat accumulation in HIV is linked to monocyte activation and systemic inflammation. The effect of zinc deficiency on body composition or metabolism is unknown.

HYPOTHESIS:

In this pilot exploratory study, our hypothesis is that short term, 16 week, zinc therapy will result in improvement in mechanisms postulated to play a role in the development and progression of HIV CVD. The endpoints are

- 1) improved serum pro-inflammatory cytokine profile
- 2) reduced oxidative stress and improved serum antioxidant status
- 3) Increased intestinal tight junctions with decreased microbial translocation

STUDY OBJECTIVES

PRIMARY: To examine whether zinc significantly affect inflammation markers in HIV-infected subjects, we will assess changes overtime in inflammation markers, and correlate these changes with changes in zinc levels

SECONDARY:

- To examine whether zinc significantly affect microbial translocation in HIV-infected subjects, we will assess changes overtime in microbial translocation markers, and correlate these changes with changes in zinc levels

-To assess the safety and tolerability of 16 weeks of zinc in HIV-infected subjects

-To ascertain whether zinc significantly affect oxidative stress in HIV-infected subjects, we will assess changes overtime in oxidative markers, and correlate these changes with changes in zinc levels

- To examine the effects of zinc on systemic blood pressure, lipid and glucose metabolism in HIV-infected subjects with good virologic control, and correlate these changes with those of inflammatory and oxidative markers

STUDY ENDPOINTS

PRIMARY: The primary inflammation markers will be sCD14, sTNF-RI, and high sensitivity C reactive protein (hs-CRP).

SECONDARY: Microbial translocation [Primarily, Lipopolysaccharide binding protein (LBP)], zinclevel, oxidative markers, safety measures (% subjects with >Grade 2 adverse events possibly or probably to study drugs), lipid levels, insulin resistance (HOMA-IR), endoPAT, and blood pressure.

INCLUSION CRITERIA:

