- Have no plans to alter antiretroviral therapy, diet or exercise or initiate structured/strategic antiretroviral treatment interruptions.
- Documentation of an HIV-1 RNA level of ≤ 400 copies/mL in the last 4 months prior to study entry
- Age at least 18 years

-Able to swallow pills.

-No diarrhea or nausea/vomiting for the last month

EXCLUSION CRITERIA

All candidates meeting any of the exclusion criteria at baseline will be excluded from study participation.

Pregnancy/lactation

Presence of inflammatory condition (besides HIV) in the last month

Regular use of agents that may affect inflammation in the last 3 months. The regular use of NSAIDS, aspirin, or statins will be allowed as long as dose has been stable for the last 3 months and is not expected to change during the study.

Presence of active neoplastic diseases requiring chemotherapy and/or use of immunosuppressive drugs

Consuming supplements containing more than the DRI level of nutrients known to affect the immune response, i.e. vitamins E, C, B6, selenium, zinc, or β -carotene and unwilling to stop.

BMI <18 kg/m².

Known cardiovascular disease

Uncontrolled diabetes

Allergy or intolerance to zinc sulfate.

Hospitalization within the previous 28 days.

Alcohol or recreational drug use which interferes with compliance

Inability or unwillingness of the individual or legal guardian/representative to give written informed consent

-Any of the following laboratory findings obtained within 14 days prior to the screening evaluation including the following:

-AST and ALT > 2.5 x ULN

-Hemoglobin < 9.0 g/dL

-GFR <50 mL/min

STUDY DESIGN

This is a pilot open labeled randomized double arm study. The duration of the study will be 16 weeks. The total sample size is 50 patients, 25 patients will be randomized to one (45 mg) capsules and 25

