Any detrimental change in a patient's condition subsequent to them entering the study and during the follow-up period should be considered an AE. When there is a deterioration in the condition for which the study treatment is being used, there may be uncertainty as to whether this is lack of efficacy or an AE. In such cases, unless the reporting physician considers that study treatment contributed to the deterioration or local regulations state to the contrary, the deterioration should be considered a lack of efficacy. Signs and symptoms of disease progression are therefore not considered AEs.

Serious Adverse Event

- A Serious Adverse Event (SAE) is an AE occurring during any study phase (eg, run-in, treatment, washout, follow-up), and at any dose of the investigational product, comparator or placebo, that fulfills one or more of the following criteria:
 - Results in death
 - Is immediately life-threatening
 - Requires inpatient hospitalization or prolongation of existing hospitalization
 - Results in persistent or significant disability or incapacity
 - Is a congenital abnormality or birth defect
 - Is an important medical event that may jeopardize the patient or may require medical intervention to prevent one of the outcomes listed above.

Any event or hospitalization that is unequivocally due to progression of disease, as determined by the investigator, must not be reported as an SAE.

The causality of SAEs (their relationship to all study treatment) will be assessed by the investigator(s)

Reporting of Adverse Events

When recording/reporting AEs, the use of diagnoses is preferred (when possible) to recording/reporting a list of signs and symptoms. However, if a diagnosis is known and there are other signs or symptoms that are not generally part of the diagnosis, the diagnosis and each sign or symptom will be recorded/reported separately.

Illiterate Subjects

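### The disease-progression exclusion leaves disease undefined, does not except death, contradicts the protocol's own AE definition, and can keep serious HIV-related events out of AE and SAE reporting

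*Combined protocol and SAP*

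**What the plan says.** The Adverse Events section of the combined protocol and SAP contains two sets of rules.

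**Inclusive rules.** The AE definition covers "the deterioration of a pre-existing medical condition following or during exposure to a pharmaceutical product, whether or not considered causally related to the product". The text then says: "Any detrimental change in a patient's condition subsequent to them entering the study and during the follow-up period should be considered an AE". An SAE is defined as an AE that meets at least one listed criterion. The first criterion is "Results in death", and inpatient hospitalisation is also listed.

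**Exclusions.** For AEs, worsening of the condition being treated is to be classed as lack of efficacy, "unless the reporting physician considers that study treatment contributed to the deterioration or local regulations state to the contrary". The next sentence concludes: "Signs and symptoms of disease progression are therefore not considered AEs". For SAEs, the rule is a prohibition: "Any event or hospitalization that is unequivocally due to progression of disease, as determined by the investigator, must not be reported as an SAE".

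No section defines disease or progression for these purposes. The Serious Adverse Event section describes no independent check on the investigator's decision, and nothing excepts death.

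**The concern.** Study staff cannot follow both sets of rules. An investigator who classes a serious event as progression is told not to report it, although the definitions just before call it an AE and, if it led to death or admission, an SAE.

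The exclusion also fits this trial poorly. Under the Inclusion Criteria, participants are on stable antiretroviral therapy with HIV-1 RNA of at most 400 copies/mL, so clinical worsening of HIV during 16 weeks is not something the plan treats as routine background. Both arms receive zinc, so there is no untreated group against which to check an attribution to progression. The plan has a secondary objective on safety and tolerability and a board asked to review adverse events. What is at stake is whether a serious HIV-related event would reach that board as a reported event.

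**Working it through.** The plan states no figure on this point, so the check is mainly textual.

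**1. One hypothetical event under both sets of rules.** Suppose a participant is admitted to hospital with an HIV-related illness and dies, and the investigator judges HIV to be unequivocally the cause.
- Inclusive rules: this is worsening of an existing condition and a detrimental change after entry, so it is an AE. It meets two SAE criteria, so it is an SAE.
- Exclusions: its signs and symptoms are not AEs. An SAE must first be an AE, so the event falls outside both definitions. Separately, the SAE sentence forbids the report.

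The two results are incompatible, and the text gives no order of precedence.

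**2. Which disease is meant.** HIV is the natural reading, since it is the condition all participants have. A cardiovascular reading is open but weaker. The Hypothesis section speaks of "improvement in mechanisms postulated to play a role in the development and progression of HIV CVD", but in a statement about mechanisms, not in a safety definition. The Exclusion Criteria list "Known cardiovascular disease", so a first cardiovascular event would be hard to call progression of a disease not known at entry.

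**3. What else could carry the event to reviewers.**
- Board report (Data Safety and Monitoring Plan; Blinding): accrual, dropout, deviations, symptoms, and clinical and laboratory findings. Deaths, hospitalisations and SAEs are not named.
- One-week IRB report: limited to effects above Grade 2 judged related to participation.
- Annual IRB renewal: adverse effects above Grade 1, with no relatedness limit in that sentence. It does not name deaths or hospitalisations.
- Health-status questionnaires at weeks 4, 10 and 16: these may record an event without making it reportable.
- Grade 4 rule (Toxicity Management): applies whatever the cause, but governs study drug and follow-up, not reporting.

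Some information would probably reach reviewers. No line guarantees it.

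**4. Effect on endpoints.** The safety endpoint is the percentage of participants with AEs above Grade 2 that are possibly or probably drug-related. An event judged unequivocally due to progression would not be judged drug-related, so it would not count even if reported. The primary endpoints are biomarkers and do not use event reports.

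**5. Scale, for illustration only.** The inputs are n = 50 in total and n = 25 per dose. The quantity is an all-cause serious-event proportion, which the protocol does not list as an endpoint.
- One event: 1/50 = 2%; 1/25 = 4%.
- Exact one-sided 95% upper bound with 0 events, 1 − 0.05^(1/n): 5.8% for n = 50 and 11.3% for n = 25.
- Exact one-sided 95% upper bound with 1 event, solving (1 − p)^n + n·p·(1 − p)^(n−1) = 0.05: 9.1% for n = 50 and 17.6% for n = 25.

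If one serious event occurred and was left out, an all-cause summary would give an upper bound of 5.8% where 9.1% is correct.

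**The case against.** The strongest reply is that the exclusion is narrow and the practical risk small. Progression must be unequivocally the cause. The AE carve-out concerns the condition for which study treatment is used, and it falls away if the physician thinks treatment contributed or local regulations say otherwise, so suspected zinc harm stays an AE. The study is short, has 50 participants, and enrols people with controlled HIV and no known cardiovascular disease. The board and the IRB receive other safety information.

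Much of this stands, and it rules out several stronger readings that a reader might infer:
- *That such events, including deaths, vanish from safety review.* The text keeps them out of AE and SAE reporting; the other channels in step 3 of the working remain.
- *That the safety endpoint would lose its most serious events.* It counts only drug-related events, so it would hardly change.
- *That cardiovascular events are plainly covered.* This is arguable at most. A first event in someone without known disease fits the AE definition as a newly developed condition.

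The reply does not remove the contradiction. The limits on the exclusion rest on the judgement of the investigator or reporting physician, with no comparator arm to test it, and none of the remaining channels requires deaths or hospitalisations to be listed.

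**Conclusion.** The point holds as a defect in safety reporting. The exclusion contradicts the protocol's AE definition and its statement on detrimental change, leaves disease undefined and does not except death. It can keep serious HIV-related events, and arguably cardiovascular events, out of AE and SAE reporting to the board.

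The expected number of such events cannot be estimated, because the documents give no HIV or cardiovascular event rate. The percentages and bounds in the working show only what one omitted event would mean in an all-cause summary; they are not shifts in a planned endpoint. The primary biomarker analysis and the sample size are unaffected, and the safety endpoint is essentially unaffected.

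The conclusion assumes that staff would apply the exclusion as written and that disease includes HIV. The passages should be reconciled, mainly because the correction is cheap and a single serious event matters in a trial of this size.

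**What to change.** - In the Serious Adverse Event section, delete the prohibition on reporting events due to progression.
- In the Adverse Event section, delete the sentence excluding signs and symptoms of progression **and** the sentence before it that classes deterioration as lack of efficacy. If only the former goes, the carve-out survives.
- State that every event meeting a listed SAE criterion is reported, including all deaths and hospitalisations.
- Record attribution to underlying disease as a category in the causality assessment of SAEs that the section already requires. This keeps the investigator's opinion without suppressing the event.
- In the Data Safety and Monitoring Plan, add deaths, hospitalisations and SAEs to the listed contents of the board's report, and match the list under Blinding.

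The cost is a few edited sentences and at most a few extra SAE forms among 50 participants. No analysis or sample-size change follows.
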